# 2. Background

The gastrointestinal (GI) tract is responsible for many functions essential to life such as digestion, absorption and excretion, all of which are under the control of its own intrinsic nervous system, the enteric nervous system (ENS) (1). The ENS is part of the autonomic peripheral nervous system and provides the intrinsic innervation of the bowel - the submucosal and myenteric plexuses are the two networks that comprise the ENS and consist of bundles of enteric neurons and glia – the enteric ganglia that are connected by nerve fibres. The ENS is essential for the autonomic regulation of gastric motility and secretion (2).

Hirschsprung's disease (HSCR) is a gut motility disorder, affecting 1 in 5000 people worldwide (3). HSCR is characterised by the absence of ganglia and nerve fibres of the ENS to various extents of the bowel: 80% of cases affect the distal colon and internal anal sphincter, but 10% of cases have total colonic aganglionosis and 1% total intestinal aganglionosis (4). Between the ganglionic and aganglionic bowel there is a transition zone. The transition zone is abnormally innervated due to a reduced number of enteric ganglia (3).

Initial presentation of neonates with HSCR typically includes distal intestinal obstruction, with symptoms including abdominal distention or vomiting and/or failure to pass meconium within the first 48hrs of life. Children with HSCR can also have difficulty feeding, severe constipation, and symptoms of HSCR- associated enterocolitis (HAEC) (5, 6).

Due to its lack of ENS, the aganglionic region of HSCR bowel is tonically contracted (3). This results in constipation and without treatment is fatal. The current gold-standard treatment for HSCR is a surgical pull-through procedure in which the aganglionic region and TZ is resected in an attempt to restore normal function.

Our group has previously demonstrated the presence of enteric nervous system progenitor cells (ENSPCs) in the aganglionic bowel of children with HSCR. ENSPCs have both a multipotent nature and proliferative capacity (7). There has been a significant amount of research into the feasibility of using ENSPCs to reduce or correct bowel dysmotility in mouse and rat models of ENS neuropathies (8-10). ENSPCs have commonly been cultured as neurospheres (9, 11-19). Neurospheres are free-floating cultures of neural stem cells that also contain neurons and glia and in the case of enteric neurospheres, ENSPCs (11, 12, 15-17).

ENSPCs cultured in neurospheres have the potential to be used as an autologous therapy for HSCR which would avoid the risk of immune rejection and can be isolated from embryonic and postnatal mouse, rat and human tissue (9, 11, 15, 17, 20). Enteric neurospheres have been shown to contain cells expressing various progenitor, neuronal and glial markers. In our lab, Almond et al. (11), demonstrated that both embryonic mouse caecum derived neurospheres and postnatal human colonic neurospheres expressed p75, Tuj1, S100, the proliferation marker BrdU and the neuronal subtype markers NOS and VIP showing that neurosphere cells were capable of proliferation and differentiation. This work was further explored in our group by Lindley and Wilkinson (15, 17, 20) and neurospheres were cultured from tissue from the aganglionic bowel of patients with HSCR. This demonstration(17), indicates the potential for autologous therapies using the patients' own aganglionic bowel due to the presence of progenitor cells that were capable of differentiation into different neuronal subtypes *in vitro*.

The transplantation of enteric neurospheres to aganglionic bowel has provided insight into the ability of such cells to rescue a model with a HSCR phenotype (9, 11, 15, 17). Using ex vivo models of

aganglionic tissue, multiple groups have demonstrated that transplanted neurospheres can integrate into tissue and differentiate into enteric glia and electrophysiologically active neurons (19).

Recently, we have found that there is an interaction in the transition zone of children with HSCR between the intrinsic ENS and the extrinsic nerves of the aganglionic bowel (21). As the transition zone is also resected during surgery for HSCR, this could provide a source of ENSPCs to use for autologous transplantation. However, transition zone neurospheres have not yet been characterised. We plan to include transition zone neurospheres in our investigation to determine whether these cells may be useful for transplantation. This forms part of our next set of experiments to investigate future therapies for HSCR.

The clinical outcomes of children with Hirschsprung's Disease have been poorly reported. Recently a core outcome set has been developed to help to standardise how children's outcomes are reported and to encourage reporting of patient's experiences as well as clinician's experiences. After pull-through 30% of patients suffering constipation or incontinence, with clear 'constipation' and 'rapid transit' phenotypes being evident (22). This may be caused by abnormal motility of the ganglionic region or by the fact that the aganglionic internal anal sphincter remains after surgery (22). Future therapies for HSCR aim to reduce long term morbidities associated with HSCR (23) but a key part of this includes drawing together children's lived experience with the findings within the laboratory. This group is currently undertaking a study of the long-term outcomes of children and adults with Hirschsprung's Disease (REC: 18/NNW/0608) and this study offers an opportunity to combine clinician and patient reported data with immunohistochemical data.

### 3. Research question

Can enteric nervous system neural progenitor cells (ENSPCs) isolated from the bowel of children with and without Hirschsprung's disease be modulated in vivo or transplanted as mature neural cells to restore function to the abnormal diseased bowel?

#### 4. Aims

The aims of this study are to answer the following questions:

- 1. How are the nerve progenitor cells different in the different sections of the bowel of children with Hirschsprung's Disease (ganglionic, aganglionic and transition zone) and do these differ to the nerve progenitor cells of children without Hirschsprung's Disease?
- 2. Do neurospheres cultured from different parts of the bowel of children with Hirschsprung's Disease have the same composition of cells within them?
- 3. Can the differentiation potential of the progenitor cells within neurospheres be manipulated via signalling pathways such as NOTCH, serotonin, endothelin 3 and Sonic Hedgehog.
- 4. Can cultured neurospheres from ganglionic, transition zone and aganglionic bowel integrate and persist in aganglionic bowel?
- 5. Do cultured neurospheres from ganglionic, transition zone and aganglionic bowel restore function to aganglionic bowel?
- 6. Are there differences in the immune profile of the ganglionic, transition and aganglionic sections of the bowel of children with Hirschsprung's Disease
- 7. Does ganglionic bowel of children with Hirschsprung's Disease have different properties which relate to their clinical experience of living with the disease?

# 5. Rationale and significance

The current gold-standard treatment for HSCR is to surgically remove the affected bowel to restore normal bowel function and enable passage of stool. However, this often has unsatisfactory outcomes: after surgery ~30% of children have constipation, incontinence or recurrent episodes of enterocolitis and 10% will need a permanent stoma (6). These outcomes are associated with psychological difficulties and significantly impact the quality of life of children and their families. Thus, there is an urgent need to improve the treatment of babies and children with HSCR.

The proposed work is a logical continuation of our previous studies (Research Ethics Committee (04/09/RE "Isolation of Human Enteric Nervous System Stem Cells" and 10/69/RE "Enteric nervous system stem cell behaviour in mature muscle models"). We have previously demonstrated that we can isolate and culture human ENSPCs and that these cells can be transplanted into aganglionic bowel to restore contractility (17). However, there are still outstanding questions on how these cells can be optimised for successful transplantation before this work can be translated to clinical trials:

- 1) What are the characteristics of the ENSPCs that can be transplanted and go on to proliferate and differentiate.
- 2) Safety: Do all these cells differentiate? Are the stem cells adequately controlled within microenvironmental niches that prevent uncontrolled growth?
- 3) What is the ideal method of transplantation? This may be whole neurospheres or single cells, with and without pharmacological agents to aid the differentiation of the ENSPCs.
- 4) Can the progenitor cells be modulated in vivo to avoid transplantation using medication?

This project is designed to begin to answer these questions using established protocols from our lab as well as incorporating new approaches such as single cell transcriptomics. Firstly, we aim to compare the progenitor populations in ganglionic, transition zone and aganglionosis bowel from children with HSCR as well as control ganglionic bowel. We will do this by examining full thickness bowel tissue sections and neurospheres with histology and single cell transcriptomic analysis. While recent publications have used single cell analysis of neuronal and glial cell populations (24, 25), it has not been carried out in progenitor populations or in HSCR samples.

Secondly, we will identify and target signalling pathways such as NOTCH, serotonin and sonic hedgehog to try and improve the potential of progenitor cells in neurospheres to differentiate when transplanted. Finally, we will optimise the method used for transplantation of neurospheres using explants of aganglionic bowel to see if we can use transplanted cells to restore function. This may involve transplanting dissociated or intact neurospheres with and without signalling pathway manipulation.

The lived experience of children with Hirschsprung's Disease is very variable, even when the length of bowel affected by Hirschsprung's Disease is the same(26). This heterogeneity may be due to the effect of differing genetic backgrounds or differences in the development of the ENS in the ganglionic part of bowel children with HSCR. These differences may reflect differences in the progenitor population and could affect the success of transplantation. Investigation of whether there are visible differences is a key step towards understanding why children have different experiences and will help to understand the translational impact of this work.

In this project we build on many years of HSCR research undertaken by our team. Our long-term goal is to use the patients' own neural stem/progenitor cell population to innervate the aganglionic bowel of infants with HSCR, thus avoiding the need for life-changing surgery and improving outcomes. To reach the point of clinical translation, a robust understanding of the developmental origin and the

properties of neural progenitor cells is essential. We have shown that neurospheres derived from bowel cell cultures contain ENSPCs that could be used as therapies (17). Therefore, it is necessary to identify any therapeutic cell population within HSCR bowel and subsequently neurospheres, and to determine the impact of external signalling pathways on the cultured cells. Furthermore, understanding the molecular mechanisms that control proliferation is a prerequisite for safe progenitor cell therapies. Linking these findings with clinical investigations, including whole genome sequencing, and outcomes is a key part in determining the potential of autologous therapies for translation to clinical practice.

# 6. Research design

This will be a prospective study.

# 7. Demographics

Infants and children undergoing intestinal resection or stoma formation. Samples will be taken from bowel resected for clinical necessity. No additional tissue will be removed.

#### 8. Research methods

#### **Inclusion criteria**

Any child undergoing therapeutic intestinal resection. Specifically, patients in which it is not necessary for all resected tissue to be sent for histopathological analysis. No additional tissue will be removed for research purposes.

#### **Exclusion criteria**

None

#### Handling of human tissue samples

Human tissue samples will be stored at the Institute in the Park, Alder Hey Children's Hospital, Liverpool and Stem Cell laboratory, Department of Molecular Physiology and Cell Signalling, Nuffield Wing, [name], University of Liverpool. Samples will be stored and disposed of according to the regulations set down in the Human Tissue Act (HTA) and under the remit of the University of Liverpool HTA governance officers.

Of the following investigations of the tissue – not every tissue will undergo each evaluation but a selection of investigations will be used depending on the study question being answered.

# Isolation of ENSC and culture of neurospheres.

The sample of bowel will be mechanically and chemically disrupted in order to produce a dissociated cell suspension which is then cultured to promote the formation of neurospheres (aggregates of stem cells, neurons and glia) using optimised cell culture and culture media. This will be performed as per our previous studies(11, 15, 17). Neurospheres will be used for subsequent analysis using histology and other techniques described below.

### Histology

As previously demonstrated, we will analyse the characteristics of the bowel tissue by looking at key markers from tissue sections and neurosphere sections. Using established techniques tissue and neurospheres will be stained using antibodies for immunofluorescence and immunohistochemistry staining such as Haematoxylin and Eosin (17, 21, 27). Such antibodies used may include those to

identify proliferating cells, neuronal and glial cells and progenitor cells. The modified thymidine analogue EdU and apoptosis assays will be used to assess proliferation and apoptosis within neurospheres in culture. This will allow us to match progenitor status with proliferative behaviour and identify aberrant responses. The stained tissue and neurospheres will be imaged using various microscopy techniques including but not limited to confocal and light microscopy.

## Single cell analysis

Following dissociation of tissue to single cells from patient tissue we would prepare for a recovery of 10,000 cells and 20,000 reads per cell. The samples will be run on a NovaSeq 6000 using an S2 flow cell for an estimated output of 3.3 billion reads, at the Centre for Genomic Research (CGR, University of Liverpool). We will use the Chromium X fixed RNA workflow which allows collection and storage of samples, followed by library preparation and sequencing of all collected samples in one day. The single cell whole-transcriptome sequencing data will be analysed using the computing program R and cells will be clustered according to their principle components using cell cluster analysis software/programmes CellRanger and Seurat. Neuronal progenitor cells will be identified and transcription factors will be interrogated for significant differences using Ingenuity Pathway Analysis. Specifically, we will be looking at the molecular profiles of individual cells to discriminate between different types of cells.

#### qPCR analysis

RNA will be extracted from tissue preparations encompassing the myenteric plexus from patient tissue samples to confirm expression of significantly upregulated markers using quantitative RT-PCR (qRT-PCR). Specimens will be analysed for the presence and quantity of markers such as SOX10, p75, Tuj, GFAP, calretinin and GLUT1 using established primers but also those identified in scRNA-Seq;  $\beta$  -actin will be used as a reference gene and each measurement will be performed in triplicate. This analysis will confirm any novel transcript expression detected by scRNA-Seq and differences in expression levels between bowel samples. To include spatial analysis of significant markers we will perform the *in situ* hybridisation technique RNAscope.

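### The qPCR plan names beta-actin as its only reference gene and describes no check that it is stable across the bowel regions being compared

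*Protocol*

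**What the plan says.** The Protocol, section 8, qPCR analysis, describes the material assayed: "RNA will be extracted from tissue preparations encompassing the myenteric plexus from patient tissue samples". The targets are "markers such as SOX10, p75, Tuj, GFAP, calretinin and GLUT1 using established primers but also those identified in scRNA-Seq", that is, six named markers plus whatever the sequencing adds. For all of them, beta-actin "will be used as a reference gene and each measurement will be performed in triplicate". The assay is meant to confirm the sequencing findings and also "differences in expression levels between bowel samples".

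Section 5 (Rationale and significance) states which samples are to be set against each other. The aim is to "compare the progenitor populations in ganglionic, transition zone and aganglionosis bowel from children with HSCR as well as control ganglionic bowel".

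Section 2 (Background) describes how those regions differ. On cell content: "HSCR is characterised by the absence of ganglia and nerve fibres of the ENS to various extents of the bowel". On tone: "the aganglionic region of HSCR bowel is tonically contracted". It adds that the transition zone has fewer ganglia than normal.

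The Protocol names no other reference gene and describes no stability check. The Statistical analysis paragraph is general and does not touch normalisation.

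**The concern.** Relative quantification reads each marker against the reference, so it assumes that the reference is expressed equally in the groups compared. Here the groups are bowel regions that differ, by the Protocol's own account, in contraction and in neural content. The RNA comes from bulk tissue, so the mix of cells supplying both marker and reference changes with region. Equal beta-actin expression is therefore an assumption that needs checking, and the plan describes no means of checking it.

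If the assumption fails in one region, the error is shared: all markers move up together, or down together, by the same factor. Modest real differences could be hidden or imitated. The shared direction could also be mistaken for consistent support across markers. The choice of reference gene is made in the Protocol itself, so this is not simply a detail left to a statistical analysis plan. No later test can recover a normaliser that was never measured.

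**Working it through.** The Protocol gives no qPCR figure, effect size, standard deviation or number per region, so there is no figure to reproduce. The check is the algebra of the method, with assumed shifts.

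**Inputs from the Protocol.** One named reference gene, triplicate measurement, six named markers plus others, and four kinds of bowel compared.

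**Assumptions.** Amplification efficiency is 100%. The regional shift *s* in the reference is 0, 0.25, 0.5 or 1.0 cycle; zero means no problem. For the false-positive rates only: two independent groups of 20, standard deviation of ΔCt 1.0 cycle, and a two-sided 5% normal test.

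**Step 1: one reference.** ΔCt = Ct(marker) − Ct(reference). Fold change of region B against region A = 2^−(ΔCt_B − ΔCt_A). Suppose a marker does not truly differ but the reference Ct is *s* cycles higher in B. Then ΔCt_B is *s* lower, and the apparent fold change is 2^s. If the reference Ct is *s* lower, it is 2^−s. The marker does not enter the expression, so the same factor applies to every marker.

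**Step 2: three references, only one shifting.** The geometric mean of three expression levels is the arithmetic mean of their Ct values, so the reference moves by s/3 and the error is 2^(s/3).

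**Step 3: false positives for a null marker.** Standard error = 1.0 × √(2/20) = 0.316 cycle. For s = 0.5 the true standardised difference is 0.5/0.316 = 1.58, and the chance of passing ±1.96 is 35.3%. With three references the difference is 0.167/0.316 = 0.53, and the chance is 8.2%.

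| Assumed shift *s* (cycles) | One reference: 2^s (2^−s) | Three references, one shifting: 2^(s/3) | False positives, one reference | False positives, three references |
|---|---|---|---|---|
| 0 | 1.00 (1.00) | 1.00 | 5% | 5% |
| 0.25 | 1.19 (0.84) | 1.06 | 12.4% | 5.8% |
| 0.5 | 1.41 (0.71) | 1.12 | 35.3% | 8.2% |
| 1.0 | 2.00 (0.50) | 1.26 | 88.5% | 18.4% |

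The false-positive columns depend heavily on the assumed spread and sample size. At s = 0.5 with one reference, the rate runs from 11.6% (SD 1.5, 10 per region) to 99.9% (SD 0.5, 50 per region). It rises with sample size, as bias does. The fold-change columns do not depend on either.

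**Step 4: do triplicates help?** A simulation used six markers with no true difference, 20 samples per region, biological SD 1.0, technical SD 0.2 and s = 0.5. The mean bias was 0.49 to 0.51 cycle for every marker, whether each measurement was made 1, 3 or 10 times. Repeat wells shrink random error within a sample; the shift lies between regions and stays.

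**The case against.** The strongest reply is that no fault in beta-actin is shown. The Background describes tone and innervation and says nothing about beta-actin transcript levels. A reader might infer that contracted bowel must express more or less of a cytoskeletal gene, but that step rests on outside knowledge and the documents do not support it. This stands: the point is an unchecked assumption, not a demonstrated bias, and zero shift is among the possibilities.

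A reader might also infer that the Protocol commits to beta-actin alone. It calls it a reference gene and does not say the only one. This stands too: what can be said is that no other is named and no check is described.

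Thirdly, a reader might infer that the study's conclusions about regional differences are at risk as a whole. The documents do not support that. Single-cell sequencing, RNAscope and flow cytometry do not use this reference, and flow cytometry is to cover the markers assessed by qPCR. None of the five milestones under Outcome measures names qPCR or a fold-change threshold, and not every sample undergoes every assay. An artefact would have to agree with the other methods to survive, and a uniform shift across unlike markers might itself be noticed. This limits the harm but does not repair the qPCR ratios. If the methods disagreed, the plan describes no means of telling a reference artefact from a real difference.

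Finally, the gain from three genes assumes that the added two are stable. Regional differences in cell content could move them as well.

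**Conclusion.** The point holds as a conditional weakness in the qPCR comparisons. One reference gene is named, its stability across the four kinds of bowel is not checked, and the only safeguard stated beside it, "each measurement will be performed in triplicate", does not address a shift between regions.

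Its size cannot be fixed from the documents. The multipliers follow exactly from the assumed shifts and 100% efficiency; the shifts themselves are not estimates. Very large differences, such as a neural marker nearly absent from aganglionic bowel, would probably survive. Modest differences, on the scale of the shift itself, are the ones exposed.

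Severity is minor to moderate. The case for acting is that the remedy is cheap, not that an error has been shown.

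**What to change.** In section 8, qPCR analysis:

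- Name at least two further reference genes alongside beta-actin. With one gene no ratio between references can be formed. With two, a change in their ratio shows that something moved but not which. Three is the smallest number that can point to the odd one out.
- Check the stability of all of them on the first samples from ganglionic, transition zone and aganglionic Hirschsprung's bowel and from control bowel.
- Normalise to the geometric mean of the genes found stable, and drop beta-actin from the set if it differs by region.

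If further reference genes are already intended, stating them and the check is enough.

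The cost is two more primer pairs, about six more wells per sample if run in triplicate (2 genes × 3 wells), and a short stability pilot across the four kinds of bowel. No new tissue is needed.
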